6.2. Medical History

6.2.1. General Medical History

Medical history will be presented as a data listing.

6.2.2. Prostate Cancer History

Prostate cancer history and curative intent treatment for prostate cancer will be summarized by treatment arm and overall for the FAS.

Years since initial diagnosis, Gleason sum at initial diagnosis and days since recurrence after curative intent treatment will be summarized using descriptive statistics. TNM status at initial diagnosis will be summarized using frequency counts and percentages.

Years since initial diagnosis is defined as the integer part of (date of first dose – date of initial diagnosis + 1)/365.25.

Days since recurrence after curative intent treatment is defined as date of first dose – date of first increased PSA value since curative intent treatment + 1.

Incomplete dates will be imputed as follows:

- If day is missing, then the day will be set to the 15th of the month.
- If month and day are missing, then the month and day will be set to July 1st.

Curative intent treatment dates for select treatments are captured for all subjects. The number of subjects receiving these treatments will be summarized using frequency counts and percentages. “Other” curative intent treatment will be collected and the number of subjects receiving these treatments will be summarized by treatment class and generic trade name, or by treatment class and drug name if generic trade name is missing, using frequency counts and percentages.

PSA values for the 6 months prior to dosing for each subject will be presented in the data listings.

6.3. Eligibility

Eligibility deviations consist of any violations of the inclusion and exclusion criteria as detailed in the protocol. Eligibility deviations and other protocol deviations captured in the CTMS will be presented in separate listings.

7. Treatments and Medications

7.1. Prior and Concomitant Medications and Non-Drug Therapies

All medications recorded on the eCRF will be coded using the World Health Organization (WHO) Drug Dictionary. Prior and concomitant medications will be summarized for the FAS by Anatomical-Therapeutic-Chemical (ATC) Class Level 4 and WHO Drug Substance preferred term (PT). Subjects may have more than one medication per drug class and preferred term. At each level of summarization, a subject is counted once if he/she reported one or more medications at that level.

Prior medications are defined as medications with a stop date occurring before the date of first dose. Concomitant medications are defined as medications with start dates occurring on or after date of first dose and before the date of last dose + 28 days. Any medication with start and stop dates that bracket the date of first dose will be summarized as both prior and concomitant medications. Medications with start dates occurring more than 28 days after the date of last dose will be defined as Follow-up medications.

For the purpose of inclusion in prior and/or concomitant medication tables, incomplete medication start and stop dates will be imputed as detailed in [Appendix C](#) of this document. Based on imputed start and stop dates, medications that clearly stopped before date of first dose

will be included in the prior medications table, and medications that clearly started on or after date of first dose and before the date of last dose + 28 days will be included in the concomitant medications table. All other medications will be included in both the prior and concomitant medications tables.

Prior and concomitant medications will be presented in a listing. Follow-up medications will be presented in a separate listing.

7.2. Study Product Exposure

Study product exposure will be summarized by treatment arm and overall for the FAS.

Number of PROSTVAC or placebo PROSTVAC injections administered, number of GM-CSF or placebo GM-CSF injections administered and duration of treatment in days will be summarized using standard descriptive statistics. The number of subjects receiving each scheduled dose will also be summarized using frequency counts and percentages.

Duration of treatment will be calculated as date of last dose – date of first dose + 1.

Dosing details will be presented in listings for all subjects

7.3. Post-Vaccination Prostate Cancer Therapy

Post-vaccination prostate cancer therapy will be collected and the number of subjects receiving therapy will be summarized by treatment class and generic trade name, or by treatment class and drug name if generic trade name is missing, using frequency counts and percentages.

8. Efficacy Analysis

8.1. Analytic Standards

8.1.1. Data Cutoff Date

Associated with each analysis is a data cutoff date. The key analyses will use the data cutoff date to censor event dates, and this may result in an event date turning into a censored date. Additional sensitivity analyses without data cutoff censoring will also be done when there has been data cutoff censoring, especially when data cutoff censoring results in loss of events.

8.1.2. One-sided P Values

Statistical programs most often report 2-sided P values, but the criterion for the key analyses described herein are based on 1-sided P values associated with 1-sided null hypotheses. The computation of a 1-sided P value requires that the effect size estimate be available and that the favorable direction be known, that is, the direction indicated in the associated alternative hypothesis.

Assume that P_2 is the 2-sided P value reported from a statistical program. The one-sided P value, P_1 , is to be computed as follows: If the effect estimate is consistent with favorable outcome then $P_1 = P_2/2$, otherwise $P_1 = 1 - P_2/2$.

8.1.3. Assessing Clinical Site Homogeneity

It is important to assess clinical site homogeneity with respect to the primary and secondary outcomes. Following is the method that will be used to obtain a descriptive assessment of clinical site homogeneity.

Assume each clinical site is identified by a unique code. It is often the case that one or more clinical sites will fail to have at least one subject assigned to each arm. All such clinical sites are to be pooled into a new pseudo clinical site with a new unique code. This new pseudo clinical site is to be used in the following analyses. A forest graph with sites or a grouping of sites will be created where the effect estimate will be displayed along with the 95% confidence interval. This graph is most effectively displayed if the estimates are sorted by estimate size.

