PSA	Prostate-specific antigen
PV	Progressive vaccinia
PVE	Post-vaccinial encephalitis
QoL	Quality of Life
RAC	Recombinant DNA Advisory Committee
RR	Respiration rate
SADR	Serious Adverse Drug Reaction
SAE	Serious adverse event

[figure not shown]
Protocol BNIT-PRV-301; Amendment 7
PROSTVAC-V/F

sc	Subcutaneous
SUSAR	Suspected Unexpected Serious Adverse Reaction
TAA	Tumor-associated antigen
TRICOM	TRICOM™, Triad of costimulatory molecules
TTP	Time to tumor progression
ULN	Upper limit of normal
VIG	Vaccinia immune globulin
VS	Vital signs

Protocol Synopsis

Protocol Title	A Randomized, Double-blind, Phase 3, Efficacy Trial of PROSTVAC-V/F ± GM-CSF in Men With Asymptomatic or Minimally Symptomatic Metastatic, Castrate-Resistant Prostate Cancer
Protocol Number	BNIT-PRV-301
IND No. / OBA Protocol Number	BB-IND 13946 / #1104-1101
NCT Number:	NCT01322490
EudraCT No.	2010-021196-85
Investigational Product	PROSTVAC-V/F
Sponsor	Bavarian Nordic, Inc. [REDACTED]
Indication	For the treatment of subjects with asymptomatic or minimally symptomatic, metastatic castration-resistant prostate cancer
CRO	[REDACTED]
Planned Sample Size	1,200 subjects (approximately)
Planned Number of Centers	250 – 300 centers worldwide
Study Type	Pivotal
Study Phase	Phase 3
Medical Monitor	[REDACTED]
Drug Safety	[REDACTED]

PROTOCOL SYNOPSIS

Background and Rationale

PROSTVAC™ (PROSTVAC-V and PROSTVAC-F; PROSTVAC-V/F) is a novel candidate prostate cancer immunotherapy for the treatment of prostate cancer. It is a viral vector based product that is administered in seven subcutaneous (sc) vaccinations, over a five month period. In a randomized controlled Phase 2 trial, PROSTVAC therapy was associated with a prolongation of survival in men with metastatic castration-resistant prostate cancer (mCRPC).

PROSTVAC is a PSA (prostate-specific antigen)-based immunization strategy. It is intended to generate immune responses to prostate specific antigens and prostate cancer cells. It uses poxviral vectors to introduce modified prostate-specific antigen (PSA) to the patient in an immunogenic manner to break self-tolerance, and thereby induce immune responses directed against prostate cancer cells.

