4.2. Randomization, Stratification, and Blinding

Block randomization will be used to randomly assign subjects in a 1:1:1 manner. Randomization will be stratified according to the following two factors, PSA (equal and above or below 50 ng/ml) and LDH (equal and above or below 200 U/L). These two stratification factors will be used to create a four-level categorical stratification variable for the following combinations of the stratification factors: (PSA < 50 & LDH < 200), (PSA < 50 & LDH ≥ 200), (PSA ≥ 50 & LDH < 200), and (PSA ≥ 50 & LDH ≥ 200). This stratification variable will be used to stratify analyses as specified subsequently.

Unblinding will be performed only in the event of a medical emergency in which the Investigator determines that knowledge of the subject's treatment assignment is necessary for effective treatment. If unblinding is required, the Investigator must contact the Medical Monitor or designee who will record who requested the unblinding, for what purpose, and for which subject, and will notify the DMC in a timely manner.

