8.2.4. Other Analyses of Survival

The following other analyses, supporting, sensitivity, or exploratory, will be performed:

- Deaths that occur after the cutoff will not be censored.
- Clinical site homogeneity will be assessed by including in the model site grouping multi-level main effect terms and also interaction terms for arm by categorical site grouping.
- The analysis will be re-run with arm by stratum interaction added to the model statement in order to assess arm by stratum interaction. If the 2-sided P value for this multiple degree-of-freedom test of homogeneity is significant at two-sided 0.10, then the stratum-specific hazard ratio estimates and confidence intervals will be computed. If the statistical criterion is not met then the test of homogeneity will be regarded as an exploratory analysis of the data collected. Thus, the outcome of the strata homogeneity test will not affect the interpretation of significance for the primary test, but will affect the way the results are presented or subsequently analyzed.
- Effect modifier analyses will be performed for putatively prognostic factors, including those explored previously in the literature as well as those hypothesized to be predictive in the context of this study. Effect modification will be assessed one factor at a time in stratified models. Each factor will be analyzed as either a natural dichotomy, a dichotomized ordered categorical with cutpoint chosen based on biologic considerations, or a continuous variable dichotomized at the overall median. A separate effect size estimate for arm and its 95% confidence interval will be computed for each level of the dichotomy using contrast statements in SAS.
- The four Kaplan-Meier estimates (arm by factor) for each of the factors analyzed as effect modifiers will be plotted on one graph.
- Regression models with multiple added prognostic covariates will be estimated. The covariates to be added will include those explored previously in the literature as well as those hypothesized to be predictive in the context of this study. Interactions will also be explored for contribution to the model.
- Subjects randomized and not initiating study intervention will be added to the FAS and the primary analyses repeated.

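### The site-homogeneity rule in SAP 8.1.3 sets no minimum site size, so about 80–150 very small sites stay as separate levels, too small for by-site hazard ratios or a dependable arm-by-site test

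*SAP*

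**What the plan says.** SAP 8.1.3 calls site homogeneity important for the primary and secondary outcomes and offers a descriptive method. It expects that "one or more clinical sites will fail to have at least one subject assigned to each arm", and for those it says: "All such clinical sites are to be pooled into a new pseudo clinical site with a new unique code". The pseudo-site is then to be used in the analyses that follow. The rule sets no minimum number of subjects or deaths for a site that stays separate. For display, "A forest graph with sites or a grouping of sites will be created", with 95% confidence intervals, but no grouping other than the pseudo-site is defined.

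SAP 8.2.4 (survival) and 8.3.2 (AWE) then assess site homogeneity by "including in the model site grouping multi-level main effect terms and also interaction terms for arm by categorical site grouping". Neither names a test statistic or a significance level for the site interaction. The two-sided 0.10 criterion in those sections belongs to the separate arm-by-stratum analysis.

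The Protocol Synopsis plans about 1,200 subjects at "250 – 300 centers worldwide". SAP 4.2 says: "Block randomization will be used to randomly assign subjects in a 1:1:1 manner". The stratification factors are PSA and LDH; site is not one of them.

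**The concern.** Having one subject in each arm is a very low bar for keeping a site separate. With one man per arm, a within-site hazard ratio can never be finite. The first death, if it occurs while both men are at risk, sends the estimate to zero or infinity; otherwise there is no estimate. The rule admits exactly such sites, and the remaining centres go into one group with nothing in common except a missing arm.

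At stake is the plan's stated check on whether the survival and AWE effects are consistent across sites. A forest plot with many non-finite estimates says little. An interaction model with over a hundred sparse levels can give opposite answers depending on the test chosen. The conduct differences that the Protocol names run by country: sipuleucel-T available only in the United States (1.2.3), clinic-only GM-CSF injection in France (2.3), and MRI as primary imaging in Germany (3.1.2.1). The pseudo-site mixes countries, and no country or region grouping is specified.

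**Working it through.** **Inputs.** 1,200 men, 1:1:1, 250–300 sites (Protocol Synopsis); 400 per arm, 534 deaths per comparison, exponential control survival with a 22-month median, the accrual pattern and the delayed effect (SAP 4.1); hazard ratio 0.68. The spread of site sizes is not in the documents and is an assumption, shown as a range.

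**Reproducing the plan's own figures.** The documents give no figure for the site analysis, so the simulation set-up was checked against SAP Table 1 (3,000 trials per case). Power was 90.7% for Case 1 (stated 90.2%), 45.0% for Case 2 (44.5%), 86.2% for Case 3 (86.1%) and 98.7% for Case 4 (98.8%). Case 3 reached 534 deaths at 5.06 years (stated 5.1). The set-up agrees with the plan.

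**Average size.** 1,200/250 = 4.8 and 1,200/300 = 4.0 men per site. For one comparison, 800/250 = 3.2 and 800/300 = 2.7.

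**Sites kept, by hand.** Allocation is taken as independent of site, and each arm is read as all three arms.
- A 4-man site has all three arms with probability 36/81 = 44%; a 5-man site, 150/243 = 62%.
- 300 equal sites of 4 men: 300 × 36/81 = 133 kept, and 1 − 133.3 × 4/1,200 = 56% of men in the pseudo-site.
- 250 near-equal sites (200 of 5 men, 50 of 4): 123.5 + 22.2 = 146 kept, and 1 − (617.3 + 88.9)/1,200 = 41% of men pooled.
- Poisson sizes, 250 sites: 1.6 men per arm per site, so 250 × (1 − e^−1.6)³ = 127 kept. For 300 sites: 300 × (1 − e^−1.333)³ = 120 kept.

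A kept 4-man site must split 2-1-1, so each comparison there rests on 2 or 3 men.

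**Simulation.** The true hazard ratio was the same at every site (1.0 or 0.68), with cutoff at 534 deaths. The Cox model had site and arm main effects plus arm-by-site terms, tested at nominal 5% (60–150 replicates per setting).

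| Site sizes | Kept sites | Men per kept site | HR zero or infinite, within-site fit | Same, joint model | Likelihood-ratio rejection |
|---|---|---|---|---|---|
| Equal | 132–148 | 4.0–4.8 | 68–78% | 35–40% | 100% |
| Poisson | about 120–128 | 5.4–6.0 | 56–62% | 30–33% | 100% |
| Skewed (gamma shape 1) | 82–100 (both skewed settings) | 8.5–12 (both) | 37–44% | 17–23% (both) | 92–99% |
| Very skewed (gamma shape 0.5) | as above | as above | 32–37% | as above | 82–95% |

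A further 2–8% of kept sites have no estimable within-site hazard ratio. The full span is therefore 32 + 2 = 34% to 78 + 8 = 86%, or roughly 35–85%. Across settings the score test rejected in 98–100% of trials and the Wald test in 0–25%. For AWE, 64–100% of kept sites have an arm at 0% or 100%, and the likelihood-ratio test rejected in 75–100%.

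**Why the tests part company.** With 146 kept sites plus the pseudo-site there are 146 site terms, 1 arm term and 146 interactions. That is 293 parameters for 534 deaths, or 1.8 deaths per parameter. In that setting the likelihood-ratio statistic averaged 1.97 times its degrees of freedom, where about 1 is expected; Wald averaged 1.07.

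**Larger groups.** With Poisson sizes, hazard ratio 0.68 throughout and 400 replicates, likelihood-ratio rejection was 5.5%, 6.0% and 5.8% with 5, 10 and 20 groups, and 14.0% with 40. With the four analysis strata it was 2.5%, 9.0%, 8.5% and 11.7%. Wald without strata gave 4.3–5.5%. No group hazard ratio was zero or infinite with 5–20 groups.

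**The case against.** The case on the other side is that this is a descriptive assessment, with confidence intervals that would show the imprecision. SAP 8.2.4 lists the models among supporting, sensitivity or exploratory analyses, and the primary logrank test is stratified by PSA and LDH only. The text also speaks of a site grouping, which need not mean a hundred separate levels. All of this stands as a limit on the consequence. It does not rescue the rule: the only grouping that 8.1.3 defines is the pseudo-site, and that is what the following analyses are told to use.

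Two stronger readings are tempting, and the documents do not support them.
- A reader might infer that most by-site hazard ratios will be zero or infinite. That holds for within-site fits with fairly even recruitment (56–78%). It fails if recruitment is skewed (32–44%) or if estimates come from the joint model (17–40%). Four men is also the average over all planned sites; kept sites average up to 12.
- A reader might infer that the planned test will declare heterogeneity in a sound trial. That is near certain for a likelihood-ratio or score test but not for Wald, and the SAP names no test or level.

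The country differences should not be overplayed. Imaging modality bears on AWE rather than survival, and nothing in the documents suggests that where GM-CSF is injected changes survival.

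**Conclusion.** The concern holds as a defect in the grouping rule. Followed as written, it keeps about 80–150 very small sites, roughly 35–85% of them without a finite within-site hazard ratio, beside one heterogeneous pseudo-site. An arm-by-site test on that grouping is unreliable: for survival, about 80–100% false rejection with likelihood-ratio or score, and about 0–25% with Wald, at nominal 5%. That two defensible tests can disagree so sharply on the same model is reason enough to settle the grouping and the test before unblinding.

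The ranges rest on assumed site-size distributions, allocation independent of site, and modest replicate numbers, which matters most for the Wald range. The type I error, success criterion and primary estimate are untouched. The change is worth making because it is cheap and turns an uninformative check into a usable one.

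**What to change.** Replace the pooling rule in SAP 8.1.3 with groups fixed before unblinding: country, with small countries merged into named regions until each group reaches a minimum number of subjects, or of blinded deaths pooled over all three arms. A minimum per arm would not work, because deaths by arm are unknown until unblinding.

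About 60 pooled deaths is one workable minimum, though the figure is a judgement. If deaths split evenly over arms, 534/2 = 267 per arm gives 3 × 267 = 801 in all, and 801/60 allows at most 13 groups. That lies within the 5–20 groups where the simulated tests stayed far closer to nominal than under the written rule. The documents give no country counts, so the list of regions must come from blinded enrolment data.

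Use the same groups for the forest plots and for the arm-by-group terms in 8.2.4 and 8.3.2. Name the interaction test and state that it is descriptive.

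The cost is a few lines of SAP text. Single-site effect estimates would no longer be shown, so an unusual single centre would not appear in the forest plot, but at this site size such an estimate carries almost no information. The by-site enrolment summary in SAP section 5 stays.

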8.2. Primary Analyses (Survival)

The survival outcome from subjects in each experimental arm, Arm V and Arm VG, will be compared separately to the survival outcome from subjects in the control arm, Arm P. If either of these comparisons passes the statistical criterion specified previously, then the trial will be regarded as having met the statistical criterion for success. This section defines the statistical method and criterion for each of these survival analyses.

The survival analysis objective is to ascertain whether the survival time distribution for subjects randomized to the experimental arm is consistent with longer survival as compared to subjects randomized to the control arm. All randomized subjects will be included in the primary survival analysis according to the randomized arm (intent-to-treat).

8.2.1. Imputation of Missing Efficacy Data

In general, there will be no imputation of missing data in efficacy analyses other than the primary endpoint (overall survival).

Imputation of the primary endpoint may depend on the date of the first occurrence of an event associated with the endpoint. When the event has yet to occur the analysis will nonetheless require an analytical date be available for the analysis. These are known as censored or truncated dates. A censored date is the date of the most recent assessment for the event for a subject for which the event of interest has yet to occur and for which additional time may lead to observation of the event of interest. A truncated date is the date of a competing event that precludes the observation of the event of interest. The distinction between designating an analytical date as censored or truncated will depend on the purpose of the analysis and will be designated for each analysis. For example, if death is the event of interest and a subject is still alive and being followed for the date of death then the date last known alive is a censored date, whereas the date a subject withdraws consent for continued follow-up of vital status (a competing event) is a truncated date. The nature of the competing event will dictate whether the

competing event is permanent. For example, the date of death for a subject who has withdrawn consent may later become known passively from governmental death records.

Dates associated with the primary endpoint with missing day of the month will be completed by imputing the missing day of the month as the 15th day of that month, provided another date to be used in the computation of an interval is not in the same month. If the day of the month is missing and the other date is in the same month, then the missing day of the month will be taken as half the distance to the beginning or end of the month (depending on expected sequence). If both dates to be used in the computation of an interval are missing day of the month then an interval of 15 days (plus or minus) will be used.

Dates associated with the primary endpoint with both month and day of month missing will be imputed as July 1 of the known year provided another date in the same year is to be used in the computation of an interval. If both the month and day of the month are missing and another date in the same year is to be used in the computation of an interval, then the missing date components will be taken as the half the distance from the other date until the beginning or end of the year (depending on expected sequence). If both dates to be used in the computation of an interval are missing both month and day of the month then an interval of 180 days (plus or minus) will be used.

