3.2. Study Endpoints

3.2.1. Primary Endpoint

The primary endpoint is overall survival (OS). OS is defined as the time between the date of randomization and the date of death due to any cause. Subjects who do not experience death or the competing events of “definite” loss to follow-up or withdrawal of consent will be right censored at the date of last contact.

OS = Date of death/competing event/censoring - date of randomization+ 1.

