8.2.2. Survival Analysis Method

Imputation of missing date parts will follow the rules previously specified. Competing events for death are “definite” lost to follow-up and withdrawal of consent for continued vital status assessments. Both of these competing events are subject to revision for an individual subject with the passage of time.

The primary analyses will be performed on the ITT set and will analyze subjects according to the randomized arm. The primary analysis will be repeated on the FAS as a sensitivity analysis.

The primary test of each endpoint will consist of a stratified logrank test for the test of the null hypothesis (STRATA <stratification-variable> / TEST=LOGRANK;). See [Section 4.2](#) for the definition of the stratification variable. The significance of the logrank test will be assessed by referring the one-sided stratified logrank test P_1 to 0.0125, and the comparison will be said to meet statistical criterion if $P_1 < 0.0125$.

Notes:

- These analyses must be stratified: Anderson et al. 2006.
- When there are competing events then censoring competing events provides a between-arm test of the event of interest: Prentice et al. 1978.

The hazard ratio for each comparison will be estimated using stratified (STRATA <stratification-variable>;) proportional hazard regression with the specification of ties handled by the exact method (TIES=EXACT option on MODEL statement). Two-sided 95% confidence interval will be reported in order to maintain consistency with the reporting of estimates from other prostate cancer studies.

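### SAP 8.2.1 does not hold an imputed death date to the date the man was last known alive, so a death can be placed before a documented contact (minor; wrong as written)

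*SAP*

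**What the plan says.** SAP 3.2.1 defines the endpoint as "OS = Date of death/competing event/censoring - date of randomization+ 1". For a man who died, the two dates in the interval are therefore death and randomization. Last contact enters only for men without an event, who "will be right censored at the date of last contact".

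SAP 8.2.1 gives the rules for partial dates:

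- **Day missing.** The rule reads "imputing the missing day of the month as the 15th day of that month, provided another date to be used in the computation"; the proviso then requires that other date to fall in a different month. If it falls in the same month, "the missing day of the month will be taken as half the distance to the beginning or end of the month (depending on expected sequence").
- **Day and month missing.** "Dates associated with the primary endpoint with both month and day of month missing will be imputed as July 1 of the known year". Where the other date lies in the same year, the imputed date is halfway from that date to the start or end of the year. As printed, the 1 July sentence and the sentence after it carry the same condition (another date in the same year) but give different rules. A *not* appears to be missing from the 1 July sentence. It is read here as applying when randomization was in a different year.

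SAP 8.2.2 carries these rules into the primary analysis: "Imputation of missing date parts will follow the rules previously specified". It adds no condition. SAP Appendix C covers only adverse event and concomitant medication dates. Neither document makes the date last known alive a lower limit for an imputed death date.

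**The concern.** The only protection of date order in SAP 8.2.1 is against the other end of the interval, which for a death is randomization. Yet the trial will hold later dates on which a man was known alive: treatment visits (Protocol 7.3), six-monthly long-term follow-up visits or calls (Protocol 7.5), and a vital status sweep with each DMC meeting (Protocol 5.1). SAP 8.2.1 itself expects that some deaths will be learned only from government records.

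Two things are at stake. A death recorded before a documented contact is impossible, and it would sit in the primary endpoint. Calendar death dates also set the analysis cutoff: SAP 12 bases the definitive analysis on data backed up to the moment the required number of deaths is reached, and SAP 8.1.1 censors events at the cutoff. Suppose a death is known only by its year, the man was reached alive on 20 October, and the cutoff is 1 September. Imputed to 1 July, he counts as dead at a cutoff after which he was documented alive.

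**Working it through.** **1. The plan's own figure.** The inputs are those of SAP 4.1: 400 per arm, exponential control with a 22-month median, hazard ratio 1 for 4 months then linear over 4 months to 0.68, accrual of 19 months' ramp plus 11 months constant, 534 deaths, one-sided 0.0125. An unstratified logrank simulation (4,000 replicates) gives power 85.3% and 5.05 years to 534 deaths. SAP Table 1, Case 3, states 86.1% and 5.1 years. The figure reproduces, so the model can be used to size the effect.

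**2. The rule applied to illustrative dates.** OS = death − randomization + 1.

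| Randomized | Last known alive | Death known as | Imputed | OS by rule | OS at least | Conflict |
|---|---|---|---|---|---|---|
| 10 Mar 2012 | 28 May 2014 | May 2014 | 15 May 2014 | 797 d | 810 d | 13 d |
| 10 Mar 2012 | 3 Nov 2014 | 2014 | 1 Jul 2014 | 844 d | 969 d | 125 d |
| 10 Jan 2013 | 20 Nov 2013 | 2013 | 6 Jul 2013 (half distance) | 178 d | 315 d | 137 d |

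The third row shows that the half-distance rule has the same gap. The largest conflicts are 31 − 15 = 16 days (day missing) and 1 July to 31 December = 183 days (month missing).

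**3. How often a partial date conflicts (assumptions).** Let the death fall uniformly in the known period of length L, and the last contact uniformly within the g days before it. The imputed point is c.

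- Day missing (L = 30.4, c = 14.5): share = (L − c)² / (2gL) = 15.9² / (2 × g × 30.4). The mean conflict is 15.9/3 ≈ 5 days.
- Year only (L = 365, c = 181): share = (L − c − g/2)/L = (184 − g/2)/365. At g = 183 the mean conflict is 184/3 ≈ 61 days.

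| Gap g | Day missing | Year only |
|---|---|---|
| 28 days (treatment visits) | 14.9% | not computed |
| 91 days (assumed, if sweeps add contacts) | 4.6% | 37.9% |
| 183 days (six-monthly follow-up) | 2.3% | 25.3% |

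At g = 183, assuming 5% of deaths day-missing and 1% year-only, 534 × (0.05 × 0.023 + 0.01 × 0.253) ≈ 2 records conflict. At 10% and 5%, 534 × (0.10 × 0.023 + 0.05 × 0.253) ≈ 8. At g = 91 the same sums give about 3 and 13.

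**4. Centring.** The 15th is close to the middle of a 30-day month (day 15.5), and 1 July is day 182 of 365 (middle 183). Over all partial dates, deaths moved earlier and deaths moved later roughly balance.

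**5. Effect on the test.** In the model of step 1, partial dates were assigned to assumed shares of deaths, equally in both arms, and the logrank test on rule-imputed dates was compared with the test on true dates (2,000 replicates each).

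| Assumed shares | Power, true dates | Power, imputed | Mean change in Z (absolute) | Maximum |
|---|---|---|---|---|
| 5% day, 1% month | 85.85% | 85.9% | 0.008 | 0.04 |
| 10% day, 5% month | 84.4% | 84.3% | 0.017 | 0.11 |

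This comparison includes all imputation error, not just the conflicting records. The cutoff was held at the true 534th death, so an effect through a shifted cutoff is not included.

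**The case against.** The strongest case for leaving the text alone is that the effect is negligible. Partial dates should be few: Protocol 5.4 tells sites to seek survival information and to pursue the death certificate. The trial is double-blind, so there is no evident reason for partial dates to differ by arm. A man whose death is found later in public records may have had no contact in his death year, and then no conflict arises. SAP 12 adds a supplemental analysis on all available data, and SAP 8.1.1 and 8.2.4 add one without cutoff censoring. All of this stands, and it limits the severity. It does not make the rule right: none of those analyses moves an impossible date.

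It could also be said that the other date in SAP 8.2.1 was meant to include last contact. The formula in SAP 3.2.1 does not use last contact for a death, so a programmer following the text would not apply it. If that is the intention, it has to be written.

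A reader might infer that the rule is wrong whenever it is used, or that it always shortens survival. Neither follows. Under the six-monthly assumption, about 98% of day-missing and 75% of year-only imputations agree with the last contact. The one-way error holds only within the conflicting subset.

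**Conclusion.** Wrong as written, and minor. The gap follows directly from SAP 3.2.1, 8.2.1 and 8.2.2. In conflicting records, survival is understated by at least the distance from the imputed date to the contact, which can reach 16 days (day missing) or 183 days (month missing).

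A reader might infer that the hazard ratio or the trial's conclusion is at risk. The documents do not support that: at the shares tried, power moves by 0.1 point or less and Z by 0.008 to 0.017 on average. Only a result lying almost on a boundary could depend on these dates. The effect through the cutoff is possible in principle but has not been sized.

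The sizes rest on assumed shares of partial dates, equal missingness across arms, and uniform timing of deaths and contacts. The documents give none of these. The existence of the gap rests on none of them.

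**What to change.** Add to SAP 8.2.1: an imputed death date may not be earlier than the date the subject was last known alive (take the later of the two), nor later than the date the death was reported. Report the number of imputed death dates by arm.

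The lower limit should be the date last known alive itself, not the day after. A day-after limit excludes death on the day of a contact. It also leaves no admissible date when the last contact falls on the final day of the known month or year, or on the day the death was reported.

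Correct the condition in the 1 July sentence in the same edit, since the month-missing rule cannot be applied as printed. This fault would remain after that correction, and the missing-day rule has it independently.

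The cost is about two sentences of SAP text, a small change to the derivation and one count in the tables. It should be done before unblinding, so that no death date has to be adjusted case by case afterwards.
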